4.5 Moment of Enrollment

Enrollment occurs when the consent form is signed and dated, randomization is complete, and the subject completes the study-assigned PE imaging study.

5. Study Procedures

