Safety Endpoints	
Defined as one or more of the following events occurring within 7 days (168 hours) of the enrollment PE imaging study:
 
 1) Time to treatment of PE > 8 hours defined as the time from study enrollment until initiation of anticoagulant therapy for PE. 2) Complications of PE imaging defined as one or more of the following occurring within 24 hours of the enrollment imaging study and requiring medical or surgical intervention: hypotension, difficulty breathing, acute pulmonary edema or hypervolemia, oral swelling, rash or puritis, abdominal pain, nausea or vomiting, altered mental status, or soft tissue contrast media or radio-isotope extravasation.

	
3) Severe health outcomes defined as one or more of the following occurring within 168 hours of the enrollment imaging study: AKI (Acute Kidney Injury Network [AKIN] 1-3); Death (any cause), renal failure, or one or more of the following requiring medical or surgical intervention: acute myocardial infarction, stroke and/or other acute arterial vascular event, in any anatomic distribution, requiring medical or surgical intervention; death with renal injury as a significant contributor defined as obvious evidence of renal failure defined by worsening azotemia with complications of renal failure including oliguria, pulmonary edema, hyperkalemia, pericardial effusion, or the need to initiate renal replacement therapy before death; identification of a venous thromboembolism (VTE, PE and/or DVT) requiring medical or surgical intervention; death from VTE and/or hemorrhage requiring medical or surgical intervention as a result of treatment for VTE.

Tertiary End-points	Mid- (occurring within 30 days) and Long-term (occurring within 1 year) severe health outcomes
Number of Subjects	
 • A total of 700 subjects will be enrolled inclusive of 600 subjects that will be randomized to CTPA or VQ imaging and 100 non-randomized subjects that will undergo CTPA.
Inclusion Criteria	
 1) Age ≥ 18 years CTPA ordered by the treating provider to evaluate PE. 2) Pre-test probability of PE $\leq 20\%$ defined using the PE Pretest Consult Score. 3) For randomization to CTPA or VQ imaging (600 subjects): AKI risk $\geq 20\%$ assessed by an AKIrisk Score ≥ 2 points 1) For non-randomized CTPA group (100 subjects): AKI risk $< 10\%$ assessed by an AKIrisk Score < 2 points.

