Patients will be identified under IRB approved waiver of authorization of release of medical records for the purpose of research. Both sites have comprehensive patient flow and computer order entry systems with real-time order alert systems that will be used to identify patients (IUH Methodist and IUH University Hospitals: Cerner©, Kansas City, MO; Eskenazi Health Hospital: Epic Systems Corporation©, Verona, WI). Notably, the applicant's research team is facile with alert systems within the EMR. As demonstration of the current success of the patient-identification process, over 2,275 of patients undergoing imaging studies for PE have been screened for an active research trial of nitric oxide to treat PE (www.clinicaltrials.gov, protocol NCT01939301, conducted by [name], a co-investigator on this proposal). The PI will leverage these existing alerts to identify potential study participants for the proposed study.

Following the first 3 months of enrollment, we plan to evaluate our enrollment process with administrative imaging logs (DORIS, Indiana University Health Department of Radiology) to evaluate potential bias in the enrollment protocol. Written, informed consent will be obtained from all study participants.

As a part of the informed consent process, participants will agree to have their creatinine and a urine dipstick measured at enrollment, and for investigators to draw and use blood and urine samples for purpose of research (to measure Cystatin-C and NGAL). Participants will also provide written informed consent to use blood and urine samples for measurement of biomarkers of AKI-risk in future work. Patients will also agree to return for a follow-up interview and have their creatinine measured between 2 and 7 days after enrollment, complete a telephone follow-up interview, and give permission to obtain their medical records to complete follow-up at 24 hours, 1 week, 30 days and 1 year.

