The subject's EMR will be screened for initial inclusion and exclusion criteria. A study investigator or coordinator will approach the potentially eligible patients for consent. If not already documented in the EMR, the study coordinator will complete the PE PreTest Consult Score and AKIrisk Scores and determine eligibility. This process may involve the treating provider for input on the risk score results. If not already performed within 7 days, an order for a chest radiograph will be placed in conjunction with the clinical team, the study coordinator will also perform a bedside urine dipstick to identify glycosuria $\geq 250\text{mg/dL}$ (1+ or greater) for patients who have not already had a urinalysis performed within 24 hours. If the patient is eligible, the coordinator will obtain the patient's written informed consent, collect basic data, and may collect urine and blood samples.

The research associate or investigator will make every attempt to talk to the patient without distractions in or around the room. Where appropriate, the investigator will personally speak to family members in quiet family rooms. Informed consent forms will be signed at the point of care by the patient. The patient will be given adequate time to make a decision. The patient will be given a copy of the informed consent document.

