5.1 Main Measurements

Collection of blood and urine samples may be obtained around enrollment and the initial follow-up (2-7-days). We will collect blood and urine samples, using standard collection methods.

Enrollment Data Collection: The study coordinator will collect the following data: age; sex; race and ethnicity; vital signs; current medications and treatments (including anticoagulation and/or thrombolysis treatment for VTE); comorbid conditions (acute and chronic); the type and severity of prior adverse reactions to iodinated contrast media; physiologic indicators of acute disease (EKG findings of cor pulmonale, indications of right-heart strain and other echocardiography data, cardiac biomarkers including troponin and brain natriuretic peptide [BNP], and lactate); and literature-derived risk factors for CIN.^{18,23,28,41,60-83} We will also record the type and volume of intravenous fluid administered 12 hours prior to and within 24 hours following the enrollment imaging study.

Baseline Creatinine Measurement If the study participant received a baseline creatinine measurement, documented in the EMR, within 24 hours of imaging around enrollment, this measurement will be used as the baseline measurement for our study. If not, we will measure a creatinine level from the blood sample collected at enrollment, if applicable.

Follow-up Creatinine Measurement The follow-up blood draw and creatinine measurement will be performed no sooner than 48 hours and no longer than 7 days (168 hours) following the enrollment imaging study using methodology established by the applicant.^{7,11,20,89} At the time of enrollment, regardless of plans for discharge or

hospitalization, study participants will be scheduled for a return visit to their site of enrollment. The patient will receive a reminder card with the date, time, and location of their follow-up appointment and a contact phone number for the study coordinator. If the patient remains hospitalized 48 hours or more following the enrollment imaging study, we will record the highest creatinine value measured during the specified follow-up time of 2-7 days, or if needed, complete the creatinine measurement. If the patient is hospitalized, but discharged prior to the follow-up period, follow-up will be completed as previously scheduled. A \$50 dollar stipend will be provided for patients that complete the return appointment as reimbursement for travel costs and time.

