5.2 Safety measurements

The study manager will monitor for occurrences of one or more of the following events occurring within 7 days (168 hours) of the enrollment PE imaging study:

- 1) Time to treatment of PE >8 hours defined as the time from study enrollment until initiation of anticoagulant therapy for PE.
- 2) Complications of PE imaging defined as one or more of the following occurring within 24 hours of the enrollment imaging study and requiring medical or surgical intervention: hypotension, difficulty breathing, acute pulmonary edema or hypervolemia, oral swelling, rash or puritis, abdominal pain, nausea or vomiting, altered mental status, or soft tissue contrast media or radio-isotope extravasation.
- 3) Severe health outcomes defined as one or more of the following occurring within 168 hours of the enrollment imaging study: AKI (Acute Kidney Injury Network [AKIN] 1-3); Death (any cause), renal failure, or one or more of the following requiring medical or surgical intervention: acute myocardial infarction, stroke and/or other acute arterial vascular event, in any anatomic distribution, requiring medical or surgical intervention; death with renal injury as a significant contributor defined as obvious evidence of renal failure defined by worsening azotemia with complications of renal failure including oliguria, pulmonary edema, hyperkalemia, pericardial effusion, or the need to initiate renal replacement therapy before death; identification of a venous thromboembolism (VTE, PE and/or DVT) requiring medical or surgical intervention; death from VTE and/or hemorrhage requiring medical or surgical intervention as a result of treatment for VTE.

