5.3 Study schedule and benchmarks

Study Events Schedule						
Procedure	Screening/ Enrollment	24 Hours after PE Imaging	≥ 48 hours and ≤168 hours	7-Day Follow-up	30-Day Follow-up	1-Year Follow-Up

			after PE imaging			
Inclusion/Exclusion Review	X					
Informed Consent	X					
Chest Radiograph	X		X			
Urine Sample	X		X			
Blood Sample/Creatinine	X		X			
Interview			X	X (If return visit not completed)		
EMR Review	X	X	X	X	X	X
Assess Primary Outcome			X	X		
Assess Secondary Outcomes		X	X	X	X	X
Asses SAEs		X	X	X		

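### Section 4.5 dates enrollment at completion of the assigned scan, so the 8-hour time-to-PE-treatment component, read as written, leaves out the wait between randomisation and the scan

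*Combined protocol and SAP*

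**What the plan says.** Section 4.5 is titled as the moment of enrollment and is the only place in the text that defines it: "Enrollment occurs when the consent form is signed and dated, randomization is complete, and the subject completes the study-assigned PE imaging study". The three conditions are joined, and the last to be met is completion of the scan.

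The first safety component in section 5.2 is "Time to treatment of PE >8 hours defined as the time from study enrollment until initiation of anticoagulant therapy for PE". The Safety Endpoints entry of the Précis has the same start: "defined as the time from study enrollment until initiation of anticoagulant therapy for PE". The second component in the same list is timed from imaging instead: "one or more of the following occurring within 24 hours of the enrollment imaging study and requiring medical or surgical intervention". The third also runs from the enrollment imaging study, for 168 hours, and includes identification of a VTE that needs medical or surgical intervention. The safety endpoint is met by any one of the three.

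Elsewhere enrollment precedes imaging:
- Section 1.6 speaks of 400 patients who are already enrolled and who afterwards undergo CTPA.
- Section 4.1 says that "participants will agree to have their creatinine and a urine dipstick measured at enrollment". The same section makes this dipstick part of settling eligibility ("the study coordinator will also perform a bedside urine dipstick to identify glycosuria"), so it comes before randomisation.
- Section 6.0 names enrollment and completion of imaging as two separate steps covered by an on-call study physician.

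The Data Analyses Plan in section 2.1 analyses all patients in the group to which they were randomised.

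**The concern.** The safety objective compares the two arms, including outcomes related to treatment of VTE, and the first component is the only endpoint that measures how quickly PE is treated. One way the arms could differ is the time taken to get the scan done: section 1.4 lists isotope preparation and specialist staff among the extra demands of VQ. If the clock starts when the scan is finished, a difference in that wait does not appear in the component, while delay after the scan (interpretation, ultrasound, crossover CTPA) does. A patient anticoagulated before the scan is complete would have a negative time and count as on time, however long after randomisation treatment began.

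There is a second consequence. If enrollment depends on completing the assigned scan, a randomised patient who does not complete it is never enrolled under 4.5, although section 2.1 analyses patients as randomised. Dropping such patients after randomisation could undo part of the balance that randomisation provides.

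**Working it through.** The plan gives no figure to reproduce. The check compares the clocks and then counts the patients who could be affected.

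**1. The two clocks.** Let W be the hours from randomisation to scan completion and T the hours from scan completion to the anticoagulant.
- Clock under section 4.5: late if T > 8.
- Clock from randomisation: late if W + T > 8.

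The two disagree when 8 − W < T ≤ 8. Counted from randomisation, the 4.5 clock has an effective limit of 8 + W hours.

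**2. Size of the shift.** The documents do not give W. The values below are assumptions for illustration.

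| Assumed W (h) | Effective limit from randomisation (h) | T counted differently (h) |
|---|---|---|
| 1 | 9 | above 7, up to 8 |
| 2 | 10 | above 6, up to 8 |
| 4 | 12 | above 4, up to 8 |
| 6 | 14 | above 2, up to 8 |

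The difference in limit between arms is W(VQ) − W(CTPA). With an assumed CTPA wait of 1 h and a VQ wait of 1, 2, 4 or 6 h, the limit is 0, 1, 3 or 5 h more lenient for VQ. If the waits are equal, the arms are treated alike and only the level of the component shifts.

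**3. Patients exposed.** Only patients treated for PE can have a first-component event. Section 1.5 gives two sources for the rate:
- 45-day VTE incidence of 3% at a pre-test risk between 2.5% and 20%: 0.03 × 300 = 9 per arm.
- PE on imaging in Table 3 of 8% (CTPA) and 10% (VQ): 0.08 × 300 = 24 and 0.10 × 300 = 30 per arm.

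That is about 9 to 30 per arm. Only those whose T falls in the last column of the table would be reclassified, and the documents do not allow that number to be estimated. Each one moves the component by 1/300 = 0.33 percentage points if all randomised patients in the arm are the denominator.

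**4. The composite.** A patient treated for a PE identified within 168 hours already scores under the third component, whichever clock the first uses. Reclassifying the first component therefore hardly changes who meets the composite.

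**5. Non-completers.** Section 2.1 allows up to 5% for patients assigned to VQ who undergo CTPA: 0.05 × 300 = 15 at most. Section 6.0 says crossover is needed only after an intermediate-risk VQ with a negative leg ultrasound. Those patients have completed VQ and satisfy 4.5, so the number left outside it should be well below 15.

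**The case against.** The strongest reply is that section 4.5 is an accrual rule, saying who counts towards the 700, and was never meant as a timestamp. Much of the other wording is loose language for a single index visit. The component concerns few patients, the composite does not depend on it, and no waiting time is documented. Most of this stands, and it limits the size of the point. It does not remove it: the section's title refers to a moment, the component is timed from enrollment, and no other time zero is given for it in the text. If 4.5 is only an accrual rule, the component's start is undefined.

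Several stronger readings are tempting but not supported:
- A reader might infer that VQ patients will be treated later and that this is hidden. Section 1.4 speaks of resources, not hours, and section 1.6 mentions longer time in the department without naming an arm or an amount.
- A reader might cite the "Screening/ Enrollment" column of the section 5.3 schedule as a further contradiction. It stands before the post-imaging columns, which also fits enrollment at scan completion.
- A reader might add the fallback baseline creatinine in section 5.1 ("If not, we will measure a creatinine level from the blood sample collected at enrollment, if applicable"). The wording around it is too loose to fix a time.
- A reader might conclude that sites have no guidance on which clock to use. Section 6.0 refers to the Appendix 1 flowchart for randomisation, outcome assessment and crossover. That figure was not available in the text reviewed, so absence cannot be asserted.
- A reader might say that the 100 non-randomised subjects can never be enrolled, because they are not randomised. That is over-literal: sections 3.1 and 4.2 plainly enroll them, and they take no part in the randomised comparison.

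**Conclusion.** The conflict in wording is real, and on the 4.5 definition the omission follows directly. The first safety component leaves out the randomisation-to-scan wait, and its effective limit becomes 8 hours plus that wait. The consequence is modest. It concerns one component, tabulated by arm, among about 9 to 30 treated patients per arm, assuming that the section 1.5 rates of 3% to 10% carry over to this trial. Bias between arms requires the waits to differ, which is plausible but not documented; the 1 to 6 hour range is an assumption. The composite safety endpoint is largely unaffected, and nothing here shifts the primary AKI result. The conflict with analysis as randomised is also real but concerns few patients. The amendment is worth making because it is cheap and protects the plan's only measure of time to PE treatment. Confidence is high on the conflict in wording and lower on its practical effect.

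**What to change.** Reconcile section 4.5 with sections 1.6, 4.1 and 6.0:
- Define time zero as randomisation, and as consent for the non-randomised group.
- Start the first safety component at the REDCap randomisation time, in both the Précis and section 5.2.
- Record scan completion time, so that delay before and after the scan can be reported separately by arm.
- State that randomised patients who do not complete the assigned scan remain in follow-up and in their assigned arm.

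The 8-hour threshold is not judged here, but the sponsor should confirm which starting point it was meant for. As a wording matter only, the contrast exclusion in section 4.3, which looks back 14 days from enrollment, should make clear that it does not refer to the study scan.

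The cost is amendment text and one extra recorded time. Randomisation runs in REDCap (section 4.4), which keeps audit trails (section 1.6), so its time should be retrievable. The downsides are that the component may show more late treatments than under the 4.5 clock and that a few non-completers must be followed.

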5.1 Main Measurements

Collection of blood and urine samples may be obtained around enrollment and the initial follow-up (2-7-days). We will collect blood and urine samples, using standard collection methods.

Enrollment Data Collection: The study coordinator will collect the following data: age; sex; race and ethnicity; vital signs; current medications and treatments (including anticoagulation and/or thrombolysis treatment for VTE); comorbid conditions (acute and chronic); the type and severity of prior adverse reactions to iodinated contrast media; physiologic indicators of acute disease (EKG findings of cor pulmonale, indications of right-heart strain and other echocardiography data, cardiac biomarkers including troponin and brain natriuretic peptide [BNP], and lactate); and literature-derived risk factors for CIN.^{18,23,28,41,60-83} We will also record the type and volume of intravenous fluid administered 12 hours prior to and within 24 hours following the enrollment imaging study.

Baseline Creatinine Measurement If the study participant received a baseline creatinine measurement, documented in the EMR, within 24 hours of imaging around enrollment, this measurement will be used as the baseline measurement for our study. If not, we will measure a creatinine level from the blood sample collected at enrollment, if applicable.

Follow-up Creatinine Measurement The follow-up blood draw and creatinine measurement will be performed no sooner than 48 hours and no longer than 7 days (168 hours) following the enrollment imaging study using methodology established by the applicant.^{7,11,20,89} At the time of enrollment, regardless of plans for discharge or

hospitalization, study participants will be scheduled for a return visit to their site of enrollment. The patient will receive a reminder card with the date, time, and location of their follow-up appointment and a contact phone number for the study coordinator. If the patient remains hospitalized 48 hours or more following the enrollment imaging study, we will record the highest creatinine value measured during the specified follow-up time of 2-7 days, or if needed, complete the creatinine measurement. If the patient is hospitalized, but discharged prior to the follow-up period, follow-up will be completed as previously scheduled. A \$50 dollar stipend will be provided for patients that complete the return appointment as reimbursement for travel costs and time.

Telephone and Medical Record Follow-up The methods planned for follow-up were developed in part by the PI and her co-investigator ([name]), have been previously published,⁸⁹ and successfully used to complete follow-up for a study of CIN incidence and subsequent outcomes.^{7,11,20,53} The methods planned for follow-up were developed in part by the PI and her co-investigator ([name]), have been previously published,⁸⁹ and successfully used to complete follow-up for a study of CIN incidence and subsequent outcomes.^{7,11,20,53} Follow-up interview will also occur during the 2-7 day follow-up appointment. For patients who did not complete the follow-up visit, we will attempt to contact the patient by telephone and/or email starting at 7-days following enrollment (to identify events occurring within 7 days of enrollment). A review of the EMR will also be performed for outcomes occurring within 24-hours, 7-days, within 30-days and within 1-year. A Social Security Death Index search will be performed for all patients that could not be contacted by telephone or email and for whom survival could not be confirmed by the medical record. In the event of a death, we will attempt to obtain a copy of the death certificate, if available.

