2.1 Primary Objectives

The primary study objective is to compare the incidence of acute kidney injury (AKI) consistent with contrast-induced nephropathy (CIN) in 600 patients with suspected PE and an AKI risk Score ≥ 2 , 300 randomized to CTPA (contrast media exposure) and 300 randomized to VQ (unexposed control) imaging. The primary outcome measure, AKI consistent with CIN. The primary outcome, AKI consistent with CIN, will be defined in both the exposed (CTPA) and un-exposed (VQ) groups using the standard literature definition for CIN:⁶⁹ an increase in creatinine $\geq 25\%$ of baseline or an absolute increase in creatinine of ≥ 0.5 mg/dL ≥ 48 hours and ≤ 168 hours of the enrollment PE imaging study.

Notably, while creatinine remains the clinical standard for identifying AKI of all types, a measurable rise in creatinine may not occur for hours to days after the initial injury. In the case of CIN, the typical peak in creatinine does not occur for 3 to 5 days, with recovery to baseline or new baseline in 7 to 14 days.^{43,44} As with other forms of AKI, in patients with normal or mild impaired renal function, a more severe injury and longer time frame are needed to detect a rise in creatinine indicative of AKI. Indeed, while many studies of CIN limit the follow-up period to 72 hours, this approach may miss 10 to 60% of cases, especially in heterogeneous populations.^{43,91-95} Even using a follow-up method that allows for variable follow-up within a 7 day period, we acknowledge that our study design is also more likely to miss cases rather than over-estimate the incidence of AKI.^{7,20,11} Our goal is to define

the potential to reduce AKI by limiting contrast media exposure. Thus, a prospective, randomized study is required.

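### The baseline creatinine is not required to precede imaging, so AKI could be under-counted, mainly in contrast-exposed patients, and the comparison pulled toward equivalence.

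*Combined protocol and SAP*

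**What the plan says.** Section 2.1 (Primary Objectives) defines the primary outcome in both arms as a creatinine rise of at least 25% "of baseline or an absolute increase in creatinine of ≥ 0.5 mg/dL ≥ 48 hours and ≤ 168 hours" after the enrollment imaging study. Every primary outcome is therefore a comparison with the baseline value.

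Section 5.1 (Main Measurements, Baseline Creatinine Measurement) gives two sources for that value:

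- First choice: a creatinine in the medical record "within 24 hours of imaging around enrollment, this measurement will be used as the baseline measurement for our study".
- Fallback: "If not, we will measure a creatinine level from the blood sample collected at enrollment, if applicable".

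Section 4.5 (Moment of Enrollment) says that enrollment occurs once consent is signed, "randomization is complete, and the subject completes the study-assigned PE imaging study".

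On timing of the injury, Section 2.1 says that "a measurable rise in creatinine may not occur for hours to days after the initial injury", and puts the typical CIN peak at 3 to 5 days.

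The primary analysis in Section 2.1 is an equivalence test with a 10-point margin, made of two one-sided tests at the 5% level. Patients are analyzed as randomized.

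**The concern.** A window stated as a number of hours from imaging, with no direction, admits values on either side of it. Section 5.1 does give a direction elsewhere: it separates fluid given before imaging from fluid given after it, and it counts the follow-up creatinine forward from imaging. The baseline rule has no such wording. Read with Section 4.5, the fallback sample is not guaranteed to precede contrast either. Nothing says which value counts when the record holds several. Section 4.1 reports that about 65% of these patients are admitted, so repeat values within a day of imaging are plausible, although the documents give no frequency.

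If a baseline drawn after contrast already contains part of the rise, the later value must climb further to qualify as AKI. The contrast-specific part of this error falls on people who received contrast and so narrows the observed difference between the arms. In a superiority trial that would cost power. Here it also favors the primary claim: a false finding of equivalence would support the hypothesis in Section 1.2 that avoiding contrast does not alter AKI risk. The 100 non-randomized CTPA patients are under the same baseline rule, so the low-risk AKI rate that is to be shown below 10% could also look better than it is.

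**Working it through.** The plan states no figure for the timing of baseline samples, so there is nothing of its own to reproduce. The check has two parts.

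**Effect on one patient.** Let *e* be the fraction by which creatinine has already risen when the baseline is drawn. To reach 25% above the drawn baseline, the follow-up value must be 1.25 × (1 + *e*) times the true pre-contrast value:

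- *e* = 5%: 1.25 × 1.05 = 1.3125, a true rise of about 31%
- *e* = 10%: 1.25 × 1.10 = 1.375, a true rise of 37.5%
- *e* = 20%: 1.25 × 1.20 = 1.50, a true rise of 50%

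The 0.5 mg/dL criterion is affected in the same way: any early rise already in the baseline is added to the 0.5 that must still be reached.

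**Effect on the trial.** Inputs:

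- Margin of 10 points and critical value 1.645 for each one-sided test (Section 2.1).
- 199 evaluable patients per arm: 300 × 0.95 × 0.70 = 199.5, from the recruitment, failure and dropout figures in Section 2.1.
- True AKI rates of 20% (CTPA) and 10% (VQ). These are assumptions: Section 2.1 gives only an overall rate below 20% and a 10-point difference. They put the truth at the margin, where equivalence should be declared about 5% of the time.
- Share *f* of CTPA baselines drawn after imaging, 10% to 30%, and share *m* = 50% of contrast-attributable AKI masked in those patients. Both are assumptions with no support in the documents.

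Only the excess over VQ is attributable to contrast, so

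observed CTPA rate = 20% − *f* × *m* × (20% − 10%)

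- *f* = 10%: 20% − 0.10 × 0.50 × 10 points = 19.5%, a difference of 9.5 points
- *f* = 30%: 20% − 0.30 × 0.50 × 10 points = 18.5%, a difference of 8.5 points

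By the normal approximation, P(declare equivalence) ≈ Φ[(0.10 − difference)/SE − 1.645]. The other one-sided test is passed almost always.

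- 19.5% vs 10%: SE = √(0.195 × 0.805/199 + 0.10 × 0.90/199) = 0.0352, so Φ(0.142 − 1.645) = 6.6%
- 18.5% vs 10%: SE = √(0.185 × 0.815/199 + 0.10 × 0.90/199) = 0.0348, so Φ(0.431 − 1.645) = 11.2%

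Applying the plan's rule to every possible pair of event counts, weighted by its binomial probability, gives the exact figures at 199 per arm:

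| CTPA rate as read (VQ 10%) | P(declare equivalence) |
|---|---|
| 20% (no masking) | 5.3% |
| 19.5% | 7.0% |
| 18.5% | 11.7% |

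The superiority analysis also loses power. By approximation at the plan's evaluable numbers of 188 and 269, power is 84.6% with no masking, 81.4% at *f* = 10% and 75.8% at *f* = 25% (both with *m* = 50%).

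**The case against.** The strongest reply is that the documents point to pre-imaging draws. The schedule in Section 5.3 lists the blood sample and creatinine under screening and enrollment and leaves the 24-hour column blank. Section 4.1 places possible blood collection at the consent step. Section 1.6 notes that an intravenous line is already in place for the imaging. Section 1.1 refers to creatinine screening before CT, so a pre-imaging value in the record is probably common. Section 4.5 can also be read as defining who counts as enrolled, not when blood is drawn; the schedule uses the same word for eligibility review and consent, which cannot follow imaging.

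Most of this stands as a description of likely practice. A reader might infer that the plan means to draw baselines after contrast, and the documents do not support that. But none of these passages is a requirement, and none governs the medical-record value, which takes precedence. The inconsistent use of the word enrollment is itself a reason to fix the text.

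The second reply concerns kinetics. By the plan's own account the rise takes hours to days and peaks at 3 to 5 days, so a value within 24 hours would usually hold only part of it. That stands, and it limits the likely effect to partial masking.

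The third is that the baseline rule is identical in both arms and the endpoint counts AKI of any cause. This also stands. AKI evolving from other causes can be absorbed into a late baseline in either arm. Up to 5% of VQ patients may cross over to contrast and are still analyzed as VQ. Fluid around imaging could lower a late baseline in either arm and push the count up.

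**Conclusion.** The gap in the wording is certain: neither baseline source is required to precede contrast, and no rule chooses among several values. The consequence is a possibility of unknown size. AKI could be under-counted, mainly in contrast-exposed patients, and that component biases the primary test toward equivalence. Under the stated assumptions (20% vs 10%, 10% to 30% post-imaging baselines, half of the contrast excess masked, 199 per arm) false equivalence goes from about 5% to about 7% to 12%. These figures illustrate scale and do not estimate what will happen.

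Two stronger readings are tempting and do not hold. One is that AKI is under-counted in the CTPA arm alone; other-cause AKI in either arm and VQ crossovers rule that out. The conclusion does not need it. If 12.5% of all AKI were masked equally in both arms (25% late baselines, half masked), the rates would read 17.5% and 8.75%. The difference would be 8.75 points, with about 10% false equivalence.

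The other is a larger effect, from masking half of all AKI in the affected CTPA patients. That would take the CTPA rate to 19% to 17% and false equivalence to 9.1% to 22.7%. It counts background AKI, shared with VQ, as if contrast had caused it, so it overstates the contrast-specific loss.

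**What to change.** In Section 5.1, for the two randomized arms and the non-randomized CTPA group alike:

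- Define baseline as the last creatinine drawn before the start of the index imaging study and within the preceding 24 hours. This also settles which value is used when there are several.
- If the record holds no such value, draw the study sample before imaging.
- Record the draw time and the imaging start time.
- Reword the fallback so that a sample taken at enrollment is consistent with Section 4.5.
- Use post-imaging baselines only in a sensitivity analysis.

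The cost is mainly protocol wording and two time fields, because venous access is already in place before imaging. The downside is that a few patients may have no pre-imaging value. They would have a missing baseline and would be handled by the missing-data method already planned in Section 2.1 (multiple imputation under missing at random).
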